
Greenphire ClinCard, which can be used as a credit or debit card. Caregivers who are consented and come to our clinic for a baseline assessment but not meet all of the entry criteria will be given \$20 for their time and inconvenience. This smaller payment reflects the generally shorter time required when a participant does not qualify for the study because the assessments stop at the point that an exclusion criterion is identified.

[figure not shown]
3.3.c.i. Inclusion/Exclusion Criteria

Inclusion Criteria: Primary Caregivers (defined as the adult who is primarily responsible for the child’s asthma management): Male or female, ages 18 to 70, primary asthma caregiver of the child, currently meeting criteria for MDD (based on DSM-4 depression symptoms for at least 2 weeks and causing clinically significant distress or impairment in social, occupational, or other important areas of functioning) based on a SCID interview.

Child: Male or female, ages 7-17 years who have a diagnosis of **persistent asthma** as classified by either of the following criteria: **A.** requirement for treatment with daily controller medication; or **B.** symptoms of persistent asthma in children not on a daily controller medication: 1. Daytime symptoms two or more days per week; 2. Rescue bronchodilator use two or more times per week; 3. Nocturnal symptoms two or more nights per month; or 4. Two or more oral steroid bursts in the last year.⁵⁶

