3.3.d.iv. Asthma Severity, Control and Outcomes: Asthma outcome measures to be used in this study will adhere to the recommended asthma clinical research core outcome measures recently proposed by the NIH's Asthma Outcomes Workshop.⁶⁰ We will incorporate information on asthma exacerbations, healthcare utilization, pulmonary function, quality of life, composite control scores, and asthma symptoms into our outcome measures. Exacerbations will be assessed by caregiver report at each study visit. Exacerbation outcomes will include systemic steroid courses, asthma-specific hospitalizations, asthma-specific emergency department visits/urgent care visits, and asthma-specific intensive care unit admissions/intubations since the last appointment. Healthcare utilization relating to each child's asthma will be assessed, including asthma-specific hospitalizations, asthma-specific emergency department visits/urgent care visits, asthma-specific outpatient visits, and asthma-specific medication use. The number of asthma-specific hospitalizations, emergency department visits and unscheduled clinic appointments by the child in the prior year and during the 1 year of the intervention will be assessed by caregiver report using a calendar to facilitate recall. This information will be supplemented with data obtained directly from the child's hospital, primary physician/asthma specialist, and pharmacy records.

Spirometry data, including % predicted of FEV₁, forced vital capacity (FVC), and FEV₁/FVC ratio will be collected on the child at all study visits using a portable spirometer (EasyOne Plus, NDD Medical Technologies, Inc. Andover, MA).

As a measurement of asthma control, the Asthma Control Test (ACT) will be administered to children ages 12+ at each caregiver depression study visit and the Childhood Asthma Control Test (cACT) will be administered to children ages 5-11.^{61, 62} The ACT and cACT tools represent a continuum of asthma control assessment tools across childhood age ranges. In both tools, a score of > 19 signifies controlled disease and scores of ≤ 19 signifies uncontrolled asthma. Thus, the scores can be combined in the data analysis.

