3.4. Statistical Analyses

Aim 1. Determine if improvement in depressive symptoms in caregivers of children with asthma predicts subsequent improvement in the child's asthma control. A CLPM for longitudinal data will be fit using a maximum likelihood SEM in order to explore reciprocal causation between asthma outcomes and depressive symptoms with lagged effect. A separate model will be constructed for each asthma outcome (e.g. CASI, ACT, steroid bursts). The full CLPM with all cross-lagged paths will test if both the asthma outcomes and depressive symptoms predict each other at subsequent visits. For each full model, paths will connect the value of the depressive symptom score (e.g. HRSD) at each visit to the asthma outcome (e.g. CASI) at each subsequent visit (e.g. 4 weeks later, 8 weeks later). Another set of paths will connect the asthma outcome at each visit to the HRSD at each subsequent visit. The full model will be compared to reduced models containing either the first set of paths or the second set. We hypothesize that the model with the first set of paths will provide a better fit than the second set. The models will be compared on goodness of fit criteria, a non-significant X^2 p-value .05 or more, fit indices .90 or more, RMSEA .05 or less, and significant path coefficients.⁶⁸⁻⁷⁵ Extensive overviews of the use of this CLPM for longitudinal data analyses are given by Cole and Maxwell and MacKinnon.^{70, 75} We will follow Cole and Maxwell's⁷⁰ guidelines for testing the proposed causal relationship, caregivers' depressive symptoms preceding child's asthma outcomes, with longitudinal data using SEM software *Mplus*. We will control for variables that might impact depressive symptoms or asthma response including age, gender and race/ethnicity. The primary analysis for this aim will use CASI scores for the child and caregiver HRSD scores. The HRSD is a widely used clinician-rated depression scale while the CASI scores take into account both asthma symptoms and asthma medication use to treat symptoms. Similar analysis will be conducted using the QIDS-SR as the depression measure and STAI as a caregiver anxiety measure. ACT scores and steroid bursts will be used as well as CASI scores in the analysis.

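### The shared cut-off of 19 supports pooling ACT and cACT as controlled or uncontrolled, but not as one score, and the models make no allowance for the change of tool at age 12

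*Combined protocol and SAP*

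**What the plan says.** Section 3.3.d.iv sets the tool by age: "the Asthma Control Test (ACT) will be administered to children ages 12+ at each caregiver depression study visit", while "the Childhood Asthma Control Test (cACT) will be administered to children ages 5-11". Section 3.3.c.i admits children on both sides of that boundary ("Male or female, ages 7-17 years who have a diagnosis of" persistent asthma). Table 2 has a single ACT/cACT row, completed at baseline and at all 13 later assessments.

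Two reasons are given for treating the tools together. The first is general: "The ACT and cACT tools represent a continuum of asthma control assessment tools across childhood age ranges". The second is the cut-off: "In both tools, a score of > 19 signifies controlled disease and scores of ≤ 19 signifies uncontrolled asthma". The text then concludes: "Thus, the scores can be combined in the data analysis".

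Section 3.4, Aim 1, builds a separate cross-lagged panel model for each asthma outcome and names ACT among them. It adds that "ACT scores and steroid bursts will be used as well as CASI scores in the analysis". Age, gender and race/ethnicity are covariates. The primary analysis of the aim uses CASI with HRSD. Aim 4 applies the same approach to each asthma outcome, without listing the outcomes.

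**The concern.** The conclusion goes further than its grounds. If both tools call a child controlled above 19, the yes/no classification can reasonably be pooled. Nothing follows about scores away from that point: two tools can agree there and still differ in mean, spread and range. Calling them a continuum asserts comparability, but no linking or equating evidence is shown.

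This matters in two ways. Between children, younger and older participants may be on different metrics in the same model. Within a child, a change of tool during follow-up could produce a step in the score that a cross-lagged model reads as a change in asthma control. The change of tool always runs from cACT to ACT and always comes later in the series, the period in which caregiver HRSD is expected to fall under treatment.

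**Working it through.** The plan gives no figure for the pooling itself. Its power figures (section 3.4: f² = 0.10 with 10 predictors and 0.31 with 78, at N = 175 and 80% power) reproduce as 0.098 and 0.309 if a 5% level is assumed. They do not depend on this point.

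**Step 1: who changes tool.** Inputs are entry at 7-17 years (3.3.c.i), cACT to age 11 and ACT from 12 at each visit (3.3.d.iv), and 52 weeks of follow-up (3.3.c). Essentially every child aged 11 at entry turns 12 during the series. No rule holds a child on the baseline tool.

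**Step 2: how many.** The documents do not give the age distribution, so three are assumed. For a normal distribution with mean m and SD s, truncated to 7 to under 18:

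- share aged 11 = [Φ((12−m)/s) − Φ((11−m)/s)] / [Φ((18−m)/s) − Φ((7−m)/s)]
- share under 12 = [Φ((12−m)/s) − Φ((7−m)/s)] / [the same denominator]

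| Assumed ages | Aged 11 at entry | Of 196 | Of 175 | Start on cACT |
|---|---|---|---|---|
| Uniform, 11 single years | 1/11 = 9.1% | 18 | 16 | 5/11 = 45% |
| Pilot Study 2 (9.8 ± 3.8) | 12.6% | 25 | 22 | 65% |
| Pilot Study 3 (9.9 ± 2.8) | 14.2% | 28 | 25 | 73% |

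For Pilot Study 3: (0.7734 − 0.6528)/(0.9981 − 0.1502) = 0.142.

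These counts are before attrition. Section 3.3.c.ii cites 75.9% retention at 12 months in TMAP. If every child lost at that rate left before turning 12, the observed switches would fall to 18 × 0.759 ≈ 14 and 28 × 0.759 ≈ 21.

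**Step 3: why one shared point is not enough.** Assume, for illustration only, that cACT = 19.5 + k × (ACT − 19.5). The tools then share the cut-off for every k. For a child whose control stays constant at ACT 14, cACT = 19.5 − 5.5k:

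- k = 1: 14.00, step at the switch 0
- k = 1.1: 13.45, step +0.55
- k = 1.25: 12.63, step about +1.4
- k = 1.5: 11.25, step +2.75

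At the cut-off the step is zero for every k. Above it the sign reverses: at ACT 22 with k = 1.5, cACT is 19.5 + 2.5 × 1.5 = 23.25, a step of −1.25. So the direction of the tool change is fixed, but the sign and size of any score step are not. The documents give no value for k and no score ranges.

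**Step 4: what the age covariate does.** Section 3.4 does not say whether age is taken at baseline or updated. Either form may absorb part of a mean difference between tools. Neither corrects a difference in spread, and baseline age cannot remove a step within a child.

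**The case against.** The strongest case on the other side has five parts.

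- The cut-off is not the only ground. The text also claims a continuum and cites development papers for both tools. This stands as a correction to any claim that the cut-off is the sole reason. But the documents show no equating result, and what the cited papers contain cannot be judged here.
- The text says scores, not raw or continuous scores, and ACT is listed beside steroid bursts, which are not a continuous scale. This stands in part. Pooling totals is the natural reading, because no transformation or dichotomy is described, but it is not spelled out.
- The switch is inferred. No sentence describes a child changing tool. That is so, but the age bands tied to each visit lead there, and nothing prevents it.
- A change of tool triggered by a birthday has no stated link to caregiver HRSD, so it would mainly add noise. This is largely right. The fixed direction and timing leave some room for a systematic effect, but the documents do not show one.
- The primary result is untouched. This stands: CASI is one instrument, described as validated from 6 to 20 years, and it carries the primary analysis of Aim 1.

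A reader might infer that every switcher shows a spurious change of some definite number of points, or that the test of Aim 1 is compromised. The documents support neither. They give no size for the difference between tools, zero is possible, and the primary outcome does not use them.

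**Conclusion.** The justification for pooling does not support pooling the scores. It supports pooling controlled/uncontrolled status. As written, the ACT/cACT models have no linking, no instrument term and no provision for children who turn 12.

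The exposure is about 9-14% of children switching and about 45-73% starting on cACT. These shares rest on assumed age distributions and on the age bands being applied at each visit. The effect on the score is unknown from the documents. The consequence is confined to a supporting outcome of Aim 1 and to Aim 4 where ACT is used. No change to the sample size follows.

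**What to change.** In 3.3.d.iv and 3.4, replace the pooling statement with the following:

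- State that the tool follows the child's age at the visit, and record which tool was used each time.
- Add a visit-level instrument indicator to the ACT/cACT models, in the equations where the score is an outcome and in those where it is a predictor.
- Report alongside these an analysis of controlled (>19) versus uncontrolled status, which the shared cut-off supports.
- Add a sensitivity analysis by instrument, or one that censors ACT/cACT data at the change of tool. This is needed because an additive indicator deals with a mean difference and not with a difference in spread.

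The data needed are already collected. The costs are a little more analysis work, some loss of information in the dichotomised analysis, and an instrument term partly confounded with age.

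Two alternatives are not recommended. Keeping children on the cACT after they turn 12 would breach the plan's own age band and change data collection. Standardising within each tool is not loss-free: it removes real differences in control between age groups and assumes both groups have the same underlying distribution.

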3.3.f. Data Management: A highly experienced data manager from the UT Southwestern P-CRI will set up the database, and monitor and advise the research team throughout the study. The data manager has managed data in much larger multisite depression research studies (e.g. TMAP, STAR*D). At the beginning of the study, a database format will be designed by the Dallas-based data management team in collaboration with [name] in Buffalo. A manual containing that format will be transmitted to Buffalo, and [name] will supervise its implementation and maintenance. Data will be maintained at the site of collection (Dallas or Buffalo). However, de-identified data (containing a study ID number but not name, SS#, or DOB) that will be used in the data analysis (e.g. depressive symptoms, asthma control) from the Buffalo site will be sent electronically to the Dallas site on a weekly basis. These data will be reviewed each week by the Dallas monitor and any errors or inconsistencies will be discussed. A data monitor from both the Dallas and Buffalo sites will review data charts and corresponding digital database content weekly and provide feedback to the PIs and research staff on data quality and recommend remediation, if necessary. To assure consistency and accuracy between sites, the data monitor from the Dallas site will travel to Buffalo every 6 months to review the data collected (e.g. charts) at the Buffalo site. The data will be checked for errors or inconsistencies, extreme values, and missing data which will be discussed and resolved.

3.4. Statistical Analyses

Aim 1. Determine if improvement in depressive symptoms in caregivers of children with asthma predicts subsequent improvement in the child's asthma control. A CLPM for longitudinal data will be fit using a maximum likelihood SEM in order to explore reciprocal causation between asthma outcomes and depressive symptoms with lagged effect. A separate model will be constructed for each asthma outcome (e.g. CASI, ACT, steroid bursts). The full CLPM with all cross-lagged paths will test if both the asthma outcomes and depressive symptoms predict each other at subsequent visits. For each full model, paths will connect the value of the depressive symptom score (e.g. HRSD) at each visit to the asthma outcome (e.g. CASI) at each subsequent visit (e.g. 4 weeks later, 8 weeks later). Another set of paths will connect the asthma outcome at each visit to the HRSD at each subsequent visit. The full model will be compared to reduced models containing either the first set of paths or the second set. We hypothesize that the model with the first set of paths will provide a better fit than the second set. The models will be compared on goodness of fit criteria, a non-significant X^2 p-value .05 or more, fit indices .90 or more, RMSEA .05 or less, and significant path coefficients.⁶⁸⁻⁷⁵ Extensive overviews of the use of this CLPM for longitudinal data analyses are given by Cole and Maxwell and MacKinnon.^{70, 75} We will follow Cole and Maxwell's⁷⁰ guidelines for testing the proposed causal relationship, caregivers' depressive symptoms preceding child's asthma outcomes, with longitudinal data using SEM software *Mplus*. We will control for variables that might impact depressive symptoms or asthma response including age, gender and race/ethnicity. The primary analysis for this aim will use CASI scores for the child and caregiver HRSD scores. The HRSD is a widely used clinician-rated depression scale while the CASI scores take into account both asthma symptoms and asthma medication use to treat symptoms. Similar analysis will be conducted using the QIDS-SR as the depression measure and STAI as a caregiver anxiety measure. ACT scores and steroid bursts will be used as well as CASI scores in the analysis.

Aim 2. Determine if improvement in depressive symptoms in caregivers of children with asthma predicts reduced unscheduled asthma-related service utilization. Separate analyses will be done for each event (ER visits, hospitalizations and unscheduled appointments). The dependent variable will be a count of the number of times the event occurred during the 52 week study period. This number will be converted to events per month to adjust for subjects who do not complete 52 weeks. The independent variables will be caregiver depressive symptoms as measured by HRSD along with site, baseline depressive symptoms, baseline asthma symptoms, and season of the year. Other baseline demographic and clinical variables (such as child's age) will be added if they improve the fit of the final model. Because the dependent variable is accumulated over the study period, caregiver HRSD will also be summarized over the study period for each subject by computing a seasonally adjusted slope of change over time during the 52 week study. All participants with two or more post-baseline HRSD measurements will be included in the analyses. Count data typically follow a Poisson distribution. Therefore, a generalized linear mixed model with Poisson link function will be used (SAS Proc GLIMMIX). Intercepts will be random effects. If an excessive number of subjects have zero events and the Poisson distribution is not appropriate (which often occurs with count data), then we will consider negative binomial models, zero-inflated Poisson models, and hurdle models. At times caregiver depression may get worse, despite treatment. Therefore, we will examine whether increases in caregiver depressive symptom severity predicts worse child asthma outcomes. The same model used above will be used here except that an indicator variable will be added to indicate if caregiver HRSD scores worsened or stayed the same during the study (zero or positive slope) versus improved (negative slope). The addition of this indicator variable will allow the relationship between change in HRSD and utilization events to differ for those who worsen or stay the same versus those who improve. This aim will be tested by the significance of this additional indicator variable. The primary analysis for this aim will use HRSD scores and ER visits (sensitive to the intervention in Pilot Study #2 and an important clinical outcome). However, similar analysis will be conducted using the QIDS-SR and STAI in place of the HRSD, and using unscheduled clinic visits and hospitalizations.

Aim 3. Determine if improvement in depressive symptoms in the caregivers of children with asthma predicts improvement in asthma-related QOL in the caregiver and child. We will use the same approach outlined above under Aim 1 above but substituting the quality of life measure (PAQOL and PACQOL) in place of the asthma control measure.

Aim 4. Examine medication adherence and child anxiety/depression as possible mediators transmitting the effect of decreased caregiver depression on asthma control and unscheduled service utilization. The goal of Aim 4 is to validate the following relationships:

Caregiver HRSD (1) → medication adherence or child anxiety/depression (2) → child asthma outcomes (3)

The relationship between (1) and (3) is considered in Aim 1. For Aim 4, two sets of CLPM analyses, (1) → (2) and (2) → (3), will be done independently as described for Aim 1. The first set of analyses will determine if caregiver HRSD improvement (1) precedes child adherence (CAMPCS scores) and anxiety/depression

improvement (SCARED, CDI-Full Length scores) (2). Separate models will be fit for adherence and anxiety/depression. The second set of analyses will determine if child adherence and anxiety/depression improvement (2) precedes child asthma outcome improvement (3). Separate models will be fit relating adherence to each asthma outcome and relating anxiety/depression to each asthma outcome (6 models altogether). Similar analysis will be conducted replacing the HRSD with the caregiver scores on the QIDS-SR and STAI.

Missing Data: The analyses described here for the Primary Aim and Secondary Aim 2 will make use of data from all available subjects, even subjects with some missing data. Also, these models are unbiased if the missing data are missing at random (MAR).⁷⁶ However, in case the MAR assumption is not satisfied, we will investigate the effect of dropouts on the final results by introducing a variable into the models to indicate whether the patient dropped out or completed.⁷¹ If this dropout status variable is significant, then sensitivity analyses will be done to determine the possible effects of dropouts on the final results.^{72-74, 76, 77} The impact of missing data in the structural equation models will be assessed by using full information maximum likelihood.⁷⁸

Power: No data exist on which to base a power analysis. However, the hypothesis tests used here involve testing regression coefficients. To obtain an approximate idea of the power of our tests, we can refer to the test of a regression coefficient that can be detected with 80% power given a sample of 175. If we conservatively assume 10 predictors for the Primary Aim and Secondary Aim 2, then an effect size of $f^2 = 0.10$ could be detected. This effect size is classified as small ($f^2 = 0.02$) to medium ($f^2 = 0.15$) according to Cohen.⁶⁹ In the full model for Secondary Aims 1, 2 and 3 there are 13 measurement occasions and approximately 200 paths; however, the hypotheses to be tested involve the 78 paths between each visit and each later visit. Given this number of predictors to be tested, an effect size of 0.31 could be detected with 80% power. This effect size is classified as medium ($f^2 = 0.15$) to large ($f^2 = 0.35$) according to Cohen.⁶⁹

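### Aim 1 lists steroid bursts, a sparse per-visit count, for the same maximum likelihood SEM and fit criteria as CASI, with no count, categorical or robust estimator stated

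*Combined protocol and SAP*

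**What the plan says.** Section 3.4, Aim 1, states the estimator: "A CLPM for longitudinal data will be fit using a maximum likelihood SEM". It then says "A separate model will be constructed for each asthma outcome (e.g. CASI, ACT, steroid bursts", so bursts go through the same approach as the two scores. The software is named ("with longitudinal data using SEM software *Mplus"), but no distribution, link or robust variant is given for any outcome. Models are to be judged on one list: "a non-significant X^2 p-value .05 or more, fit indices .90 or more, RMSEA .05 or less, and significant path coefficients".

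Bursts are not primary. The plan says "The primary analysis for this aim will use CASI scores for the child and caregiver HRSD scores", and then "ACT scores and steroid bursts will be used as well as CASI scores in the analysis".

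Section 3.3.d.iv shows what kind of variable this is: "Exacerbation outcomes will include systemic steroid courses, asthma-specific hospitalizations" and similar events, reported by the caregiver at each visit for the time since the previous one. With visits every 4 weeks, that is a count over about 4 weeks.

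Section 3.4, Aim 2, treats comparable events differently. It reasons that "Count data typically follow a Poisson distribution", chooses a Poisson mixed model, and names negative binomial, zero-inflated and hurdle models if zeros are excessive. It applies this to ER visits, hospitalizations and unscheduled appointments. Steroid bursts are not on that list.

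**The concern.** A count that is zero at most visits is not close to normal. Its variance moves with its mean, and some children are likely to have persistently higher rates than others. Model chi-square and RMSEA rest on comparing observed with model-implied covariances, and their reference distributions assume roughly normal data. If bursts are fitted as a continuous variable, the fit test can condemn a correct model and some standard errors can be wrong. Aim 1 is decided by comparing a full model with two reduced models on these criteria, so a faulty fit test would distort the comparison for this outcome.

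If the analyst instead declares bursts as a count in Mplus, the listed chi-square and RMSEA criteria may not apply, and the plan does not say what replaces them. Either way the choice is left until the data are in hand.

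**Working it through.** **The plan's own figures.** Section 3.4 (Power) gives detectable f² of 0.10 (10 predictors) and 0.31 (78 predictors) at N = 175 and 80% power. Using a joint F test with noncentrality λ = f² × N, denominator df N − u − 1 and alpha 0.05 (assumed; none is stated):

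- u = 10: λ = 0.10 × 175 = 17.5, df 10 and 164, power 0.810; 80% is reached at f² = 0.098.
- u = 78: λ = 0.31 × 175 = 54.25, df 78 and 96, power 0.802; 80% is reached at f² = 0.309.
- The path count is 13 × 12 / 2 = 78.

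Both figures reproduce. They come from normal linear regression and say nothing about a count.

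**How sparse the count is.** No expected burst rate is given. The only anchor is one of several alternative entry criteria in 3.3.c.i, two bursts in a year: 2 / 13 = 0.154 per 4-week visit. I therefore take 0.05 to 0.30 per visit as an assumed range. Under a Poisson model the share of zero visits is exp(−rate):

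| Rate per visit | Per year (× 13) | Zero visits | Expected bursts per visit, N = 175 |
|---|---|---|---|
| 0.05 | 0.65 | 95% | 8.75 |
| 0.154 | 2.0 | 86% | 27 |
| 0.30 | 3.9 | 74% | 52.5 |

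**The chi-square fit test.** The simulation used N = 175, 13 occasions, 0.154 bursts per visit and lag-1 dependence 0.3. The lag-1 model, which is correct here, was tested against all earlier lags by X² = Σ N ln(RSS of the lag-1 model / RSS of the all-lags model), with df = 1 + 2 + … + 11 = 66. At a nominal 5%:

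- normal data: 7.3% rejected;
- two count processes with the same lag-1 mean: 17.8% and 23.2%, which is 17.8 / 7.3 = 2.4 and 23.2 / 7.3 = 3.2 times the normal figure.

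A second simulation that included HRSD gave 27% to 32% against 15% for normal data when HRSD had an effect, but 13% to 22% when it had none. The over-rejection is a tendency, not a constant.

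**Standard errors.** Bursts at one visit were regressed by normal maximum likelihood on three earlier HRSD values, three earlier burst counts and three covariates (N = 175), with and without child-level overdispersion (gamma, variance 1). The table gives the mean model standard error divided by the true SD of the estimate. A normal outcome gives 0.96, because maximum likelihood divides by N.

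| Path | Condition | Ratio |
|---|---|---|
| HRSD to bursts | no effect | 0.94–0.98 (rejection 4.9–6.6%; normal outcome 6.2%) |
| HRSD to bursts | effect, symmetric HRSD | 0.80–0.96 |
| HRSD to bursts | effect, right-skewed HRSD | 0.31–0.80 |
| HRSD to bursts | effect, left-skewed HRSD | 1.11–1.19 |
| Bursts to HRSD | all | 0.91–0.99 (rejection about 5–7%) |
| Bursts to later bursts | child-level overdispersion | 0.41–0.70 |

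Effects were log rate ratios of 0.3 to 0.6 per SD of HRSD. Sandwich standard errors for the burst-to-later-burst path at 0.05 per visit still reached only 0.63 to 0.69 of the true SD. Rates, dispersion, effects and HRSD shapes are all assumptions.

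**The case against.** A reader might infer that standard errors for bursts will be too small throughout, and that the HRSD-to-burst tests are therefore over-confident. The documents do not support that. Stacking all visits in one lag-1 regression and ignoring the child does give 95% intervals that cover only 80% to 92% in several settings, but the plan does not propose that regression. Aim 1 describes separate paths from each visit to each later visit, with one row per family. Visit-specific equations under those settings (0.08 or 0.15 bursts per visit) covered 93% to 96%. A further run over 0.08 to 0.30 covered 92% to 96%, against 93% for a normal outcome. A normal outcome with a child effect also under-covers in the stacked regression (86% to 90%), so that loss comes mainly from ignoring the child, not from the count.

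The remaining objections are fair. The plan never says that bursts will be treated as normal; that is inferred from the single approach and the covariance-based criteria. Mplus can fit counts, so the text is underspecified, not plainly wrong. No rate, dispersion or effect in the simulations comes from the documents. Bursts are an additional outcome, and exacerbations are already one domain of CASI (3.3.d.iv).

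What survives is the gap itself, the behaviour of the fit test, and the understated errors on the burst-to-later-burst paths.

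**Conclusion.** The point holds as a minor one. Aim 1 lists a sparse per-visit count for a maximum likelihood SEM and its chi-square, fit-index and RMSEA rules, and states no estimator suited to it, while Aim 2 already has a suitable model class for similar events. At 0.154 bursts per visit the fit test rejected a correct model roughly two to three times as often as for normal data, though the excess was not consistent when HRSD had no effect. Burst-to-later-burst standard errors were clearly too small under overdispersion. For the HRSD-to-burst paths that carry the hypothesis, there was no material count-specific understatement under no effect. With an effect, the direction of error depends on the shape of the HRSD distribution. The sizes rest on the assumed inputs listed above. The CASI and HRSD analysis, which is primary for Aim 1, is not touched.

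**What to change.** For steroid bursts only, choose one of these in the plan before the data are analysed:

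1. Declare bursts as a count (or as binary, any versus none) in the Mplus cross-lagged model, keeping both directions. Compare the full model with each reduced model by likelihood-ratio test. The two reduced models are not nested in each other, so compare them by AIC or BIC. State that the chi-square and RMSEA criteria are not used for this outcome.
2. Report an interval-level Poisson or negative binomial mixed model, with a random intercept and HRSD at the previous visit, as the test of the HRSD-to-burst direction.

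Robust standard errors added to the continuous model may not be enough at low rates. The same choice should apply to any Aim 4 model that uses bursts.

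The change is to the text of the plan and needs no new data or software. The first option loses the SEM fit indices for this outcome. With perhaps 9 bursts per visit at the lowest assumed rate, the full set of visit-specific paths may not be estimable, so name a fallback such as paths held equal over time. The second option tests one direction only and so gives up the reciprocal comparison for bursts.
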